#### 8.5.2. Presentation of Pharmacokinetic Data

If the actual time of sample collection deviates from the nominal time by more than  $\pm 10\%$ , the plasma concentration will be flagged and excluded from the summary statistics.

Individual concentrations deemed to be anomalous will be flagged in the listings and excluded from the summary statistics.

For plasma concentration data the following rules will apply:

- Values that are BLQ will be set to 0 for the calculation of summary statistics.
- If the embedded BLQ value is considered anomalous within the concentration-time profile, this value will be excluded from the summary statistics.
- Where there is NR, these will be set to missing.
- If there are less than three values in the data series, only the min, max and N will be presented. The other summary statistics will be denoted as not calculated (NC). BLQ is considered a value.
- If the values are BLQ, then the arithmetic mean, arithmetic SD, median, min and max will be presented as zero, 0 and the geometric mean and geometric coefficient of variation (CV%) will be denoted as NC.
- Arithmetic mean or median values that are BLQ will be presented as 0, and the geometric mean and geometric CV% will be denoted as NC.

For PK parameters the following rule will apply:

- For the calculation of summary statistics of PK parameters, all non-reportable and NC values in a data series will be set to missing.
- AUCinfand AUClast will be set to NC if they were calculated using fewer than three concentrations, and/or three concentrations if the last is Cmax.
- Geometric mean and coefficient of variation will not be calculated for  $t_{last}$  or  $t_{max}$ .

## 8.5.3. Pharmacokinetic Statistical Methodology

All PK concentrations and parameters will be listed.

Summary tables, mean (+ standard deviation [SD]) figures, overlaying individual figures, and individual figures by treatment and time postdose will be provided for plasma PK concentrations. All figures will be produced on both linear and semi-logarithmic scales.

Summary tables by treatment will be provided for all PK parameters, with the exception of regression-related PK parameters.

#### Bioequivalence:

A statistical analysis will be conducted to investigate the bioequivalence of 960 mg sotorasib administered orally as 3 x 320 mg tablets (test 1) to 960 mg sotorasib administered orally as 8 x 120 mg tablets (reference treatment) for  $AUC_{last}$ ,  $AUC_{infi}$  and  $C_{max}$ . Data from the entire study population will be used for this analysis.

The natural log (ln)-transformed PK parameters will be analyzed using a mixed model. The model will include treatment, period, and sequence as fixed effect and subject nested within sequence as a random effect.

For AUClast, AUCinf and Cmax separately, the least squares mean (LSM) for each treatment, difference in LSMs between the test 1 and reference treatments, and corresponding 90% confidence interval (CI) will be calculated; these values will then be backtransformed to give the geometric least square mean (GLSM), ratio of GLSMs, and corresponding 90% CI.

Additionally, the pooled estimate (across all treatments) of the within-subject CV will be calculated, and residual plots will be produced to assess the adequacy of the model(s) fitted.

It will be concluded that the test treatment is bioequivalent to the reference treatment if, for  $C_{max}$  and AUCs, the 90% CI for the ratio of GLSMs is completely contained within the predefined interval of (0.8000, 1.2500). This procedure is equivalent to Schuirmann's two one-sided tests at the 0.05 level of significance.

Examples of the SAS code that will be used are as follows:

#### Mixed Model Analysis

```
proc mixed data = <data in>;
  by parcatln parcatl pkday paramn param;
  class trtan aperiod trtseqp usubjid;
  model lpk = trtan aperiod trtseqp / cl residual ddfm = kr;
  lsmeans trtan / cl pdiff = control('2') alpha = 0.1;
  random intercept / subject = usubjid(trtseqp);
  ods output lsmeans = <data out>;
  ods output diffs = <data out>;
  ods output covparms = <data out>;
run;
```

#### **Food Effect:**

A statistical analysis will be conducted to investigate the food effect for 960 mg sotorasib administered orally as 3 x 320 mg tablets under fed condition (test 2) to 960 mg sotorasib administered orally as 3 x 320 mg tablets under fasted condition (test 1) for  $AUC_{last}$ ,  $AUC_{inf}$  and  $C_{max}$ . Data from 14 subjects who are enrolled in Period 3 will be used for this analysis.

The natural log (ln)-transformed PK parameters will be analyzed using a mixed model. The model will include treatment as fixed effect and subject nested within sequence as a random effect.

Page 41 of 47

For  $AUC_{last}$ ,  $AUC_{infi}$  and  $C_{max}$  separately, the least squares mean (LSM) for each treatment, difference in LSMs between the test 1 and test 2, and corresponding 90% confidence interval (CI) will be calculated; these values will then be backtransformed to give the geometric least square mean (GLSM), ratio of GLSMs, and corresponding 90% CI.

Additionally, the pooled estimate (across all treatments) of the within-subject CV will be calculated, and residual plots will be produced to assess the adequacy of the model(s) fitted.

Examples of the SAS code that will be used are as follows:

## Mixed Model Analysis

```
proc mixed data = <data in>;
  by parcatln parcatl pkday paramn param;
  class trtan usubjid;
  model lpk = trtan / cl residual ddfm = kr;
  lsmeans trtan / cl pdiff = control('2') alpha = 0.1;
  random intercept / subject = usubjid(trtseqp);
  ods output lsmeans = <data out>;
  ods output diffs = <data out>;
  ods output covparms = <data out>;
run;
```

# 8.6. Safety and Tolerability Assessments

#### 8.6.1. Adverse Events

All AEs will be coded using the Medical Dictionary for Regulatory Activities (MedDRA) Version 24.0 (or higher if a new version is issued during the study; see the DMP for more details). All AEs will be assigned a severity grade using Common Terminology Criteria for Adverse Events (CTCAE) Version 5.0 (or higher if a new version is issued during the study; see the protocol for more details).

A treatment-emergent adverse event (TEAE) will be defined as an AE that starts during or after dosing, or starts prior to dosing and increases in severity after dosing within each period.

A treatment-related TEAE will be defined as a TEAE with a relationship related to the study treatment, as determined by the investigator.

All AEs will be listed. In addition to the data recorded in the database, the listings will include derived onset time and duration. Onset time will be calculated from the time of dosing for TEAEs only.

The frequency of subjects with TEAEs and the number of TEAEs will be summarized for the following categories:

- TEAEs (overall, serious, leading to discontinuation, and leading to death) by treatment
- TEAEs by severity and treatment

• Treatment-related TEAEs (overall, serious, leading to discontinuation, and leading to death) by treatment

• Treatment-related TEAEs by severity and treatment

The frequency of subjects will be summarized separately for TEAEs and treatment-related TEAEs by the following:

- System organ class, preferred term, and treatment
- Preferred term and treatment

For the AE data the following rules will apply:

- For the derivation of treatment-emergent status (applicable to all AEs): If the start date/time of an AE is incomplete or missing, an AE will be assumed to not be a TEAE, unless the incomplete start date/time or the end date/time indicates an AE started after dosing.
- For the derivation of treatment-related status (applicable to TEAEs only): If the study treatment relationship for a TEAE is missing, a TEAE will be assumed to not be a treatment-related TEAE.
- For the derivation of onset time (applicable to TEAEs only): If the start date/time of a TEAE is missing, onset time will not be calculated. If the start date/time of a TEAE is incomplete, where possible, the minimum possible onset time will be calculated and presented in '≥DD:HH:MM' format (eg, if the date/time of dosing is 01MAY2019/08:00 and recorded start date/time of a TEAE is 03MAY2019, then the minimum possible onset time will be calculated by assuming a TEAE started at the first hour and minute of 03MAY2019 [03MAY2019/00:00], thus will be presented as onset time ≥01:16:00 in the listing). If the start date of a TEAE is the same as the date of dosing but the start time of a TEAE is missing, an onset time will be presented as '≥00:00:01'. Any clock changes will be accounted for in the derivation.
- For the derivation of duration (applicable to all AEs): If the end date/time of an AE is missing, duration will not be calculated. If the start or end date/time of an AE is incomplete, where possible, the maximum possible duration will be calculated and presented in '≤DD:HH:MM' format (eg, if the start of an AE date/time is 01MAY2019/08:00 and its recorded end date/time is 03MAY2019, then the maximum possible duration will be calculated by assuming an AE ended at the last hour and minute of 03MAY2019 [03MAY2019/23:59], thus will be presented as duration ≤02:15:59 in the listing). Any clock changes will be accounted for in the derivation.
- For the calculation of TEAE summary statistics: If the severity of a TEAE is missing, that TEAE will be counted under the 'missing' category.

• For the calculation of TEAE summary statistics: If a subject experienced multiple TEAEs with the same preferred term for the same treatment, this will be counted as 1 TEAE for that treatment under the maximum severity recorded.

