## 3. INVESTIGATIONAL PLAN

## 3.1. Overall Study Design and Plan

This will be an open-label, multi-center (United States), crossover, 3-period bioequivalence study to compare the PK of a single oral dose of 960 mg sotorasib administered as 3 x 320 mg tablets (test 1) under fasted condition to a single oral dose of 960 mg sotorasib administered as 8 x 120 mg tablets (reference) under fasted condition and the PK of 960 mg sotorasib administered as 3 x 320 mg oral tablets following a high-fat meal (test 2) to 960 mg sotorasib administered as 3 x 320 mg oral tablets under fasted condition (test 1) in healthy male subjects and healthy female subjects. Approximately 146 subjects will be enrolled to ensure that at least 132 subjects complete the study.

Potential subjects will be screened to assess their eligibility to enter the study within 28 days prior to the first dose administration. Subjects will be admitted into the Clinical Research Unit (CRU) on Day -1 and be confined to the CRU until discharge on Day 6 or Day 9. On Day 1, subjects will be randomized to Group 1 or Group 2. Each subject will receive one administration of 960 mg sotorasib administered orally as 3 x 320 mg tablets (Treatment A: test 1) and one administration of 960 mg sotorasib administered orally as 8 x 120 mg tablets (Treatment B: reference) in either Period 1 or Period 2 according to their assigned group. Each subject will receive both treatments following an overnight fast according to the treatment sequence in Table 1. On Day 7, 14 subjects in either Group 1 or Group 2 will proceed to Period 3 and receive one additional administration of 960 mg sotorasib administered orally as 3x 320 mg tablets with a high-fat meal (Treatment C: test 2).

Group	Period 1 (Day 1)	Period 2 (Day 4)	Period 3 (Day 7)
1	Treatment A	Treatment B	Treatment C
2	Treatment B	Treatment A	

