#### Figure 1: Study Schematic

Abbreviations: EOS = End of Study; ET = Early Termination; N = number of subjects \*Subjects will receive a single dose in each treatment period, on Days 1, 4, and 7.

\*\* Subjects will be discharged on Day 6 or Day 9 according to their treatment assignment.

The total duration of study participation for each subject (from Screening through end of study [EOS]) is anticipated to be approximately 5 weeks.

The start of the study is defined as the date the first enrolled subject signs an Informed Consent Form (ICF). The point of enrollment occurs at the time of subject number allocation. The end of the study is defined as the date of the last subject's last assessment (scheduled or unscheduled).

A Schedule of Assessments is presented in Appendix 9.

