## Protocol Amendment 2 Labcorp Drug Development Study: 8471128

c Electrocardiograms will be collected after the subject has rested in the supine position for at least 5 minutes, and will be obtained prior to the scheduled blood draws at: Screening; Check-in; prior to and 0.5, 2, and 4 hours following sotorasib administration on Days 1, 4 and 7; and EOS or ET. The 30-minute postdose ECG measurement will have a collection window of  $\pm$  2 minutes, the 2-hour postdose ECG measurement will have a collection window of  $\pm$  5 minutes, and the 4-hour postdose ECG measurement will have a collection window of  $\pm$  10 minutes.

d Vital signs measurements (supine blood pressure [BP], supine heart rate, respiratory rate, and oral body temperature) should be carried out prior to having blood drawn. Screening; Check-in; prior to sotorasib administration on Days 1, 4 and 7; 1 and 24 hours following sotorasib administration on Days 1, 4 and 7; and EOS/ET. Heart rate and BP will be measured using the same arm for each reading after the subject has been resting in the supine position for at least 5 minutes.

e Clinical chemistry (fasted at least 8 hours), hematology, and urinalysis.

- f eGFR will be calculated using the Modification of Diet in Renal Disease equation.
- g A full physical examination at Check-in and a symptom-directed physical examination at EOS/ET.

h Dose administration of sotorasib is to occur during the mornings of Days 1, 4 and 7 in accordance with the formulation of sotorasib administration specific to their treatment (Treatment A, Treatment B or Treatment C).

 Blood samples for determination of sotorasib plasma concentrations will be collected: Predose (Hour 0), 0.5, 1, 1.5, 2, 2.5, 3, 3.5, 4, 5, 6, 8, 10, 12, 24, 36, and 48 hours postdose following administration of sotorasib on Days 1, 4 and 7. The PK sample collected at 30 minutes postdose will have a sampling window of  $\pm 2$  minutes, samples collected from 1 through 3 hours postdose will have a sampling window of  $\pm 5$  minutes, samples collected from 4 through 10 hours postdose will have a sampling window of  $\pm 10$  minutes, and samples collected from 12 through 48 hours postdose will have a sampling window of  $\pm 20$  minutes. Times of all PK samples will be recorded to the nearest minute.

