j Adverse events will be recorded from initiation of study treatment on Day 1 until EOS completion. Serious adverse events will be recorded from the time the subject signs the ICF through 30 days after the last dose of study treatment or the EOS (whichever is later).

k Prior and concomitant medication administration will be recorded beginning at informed consent. In addition, all Investigator-approved medications taken by a subject within 30 days or 5 half-lives (whichever is longer) prior to enrollment administration for over-the-counter or prescription medications, and 30 days prior to enrollment for herbal medicines (eg, St. John's wort), vitamins, and supplements, will be recorded on the subject's electronic Case Report Form.

Assessment to be performed at the EOS or if a subject is withdrawn early from the study.

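### The by-treatment TEAE tables in SAP 8.6.1 use unequal observation windows, so non-serious events after fed Treatment C are under-counted against A and B to a degree set by onset timing

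*SAP*

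**What the plan says.** Protocol Appendix 9, footnote h, sets the dosing days: "Dose administration of sotorasib is to occur during the mornings of Days 1, 4 and 7". Only the 14 Period 3 subjects receive the Day 7 dose, which is Treatment C, and Protocol 5.6 says that Period 3 is not randomised. The note to Protocol Figure 1 adds: "Subjects will be discharged on Day 6 or Day 9 according to their treatment assignment".

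Appendix 9, footnote j, fixes collection of non-serious events: "Adverse events will be recorded from initiation of study treatment on Day 1 until EOS completion". Protocol 7.2.1 ends it at the same point. Serious events run longer: "Serious adverse events will be recorded from the time the subject signs the ICF through 30 days after the last dose", or to end of study if that is later.

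SAP 8.6.1 defines a TEAE as an "AE that starts during or after dosing, or starts prior to dosing and increases in severity after dosing within each period". It then summarises numbers of subjects and of events for "TEAEs (overall, serious, leading to discontinuation, and leading to death) by treatment", and again by severity, relatedness, system organ class and preferred term. It sets no upper limit on time since dose, no common window and no adjustment for observation time. It does not say which treatment receives an SAE that starts after end of study. SAP 8.1 runs the listings only to study completion or discontinuation. SAP 8.6.6 plans no inferential safety analysis.

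**The concern.** A by-treatment count can be compared across columns only if each treatment was watched for a similar time. Here the time watched depends on whether another dose followed. Randomised order largely evens this out between A and B. Nothing can even it out for C, because every C dose is the subject's last.

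Adverse events are a secondary endpoint, and the same tables set C beside A and B. Protocol 1.2 reports a 1.38-fold fed AUCinf at 360 mg, so a reader may look at the C column for extra events with food. The shorter window pushes that column down. Because the safety results are descriptive, the counts are what will be read, and the absence of a test does not remove the bias.

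**Working it through.** **Inputs.** Doses on Days 1, 4 and 7; end of study on Day 6, or Day 9 with Period 3 (Protocol 3.1, Figure 1, Appendix 9). Planned enrolment is 146, with 73 per sequence (Protocol 8.1). Fourteen subjects enter Period 3; their split between the two groups is not fixed.

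**Check on the 48 h.** The plan states no observation window per treatment, so there is no figure of its own to reproduce. The PK schedule gives a cross-check. Samples are taken at "24, 36, and 48 hours postdose following administration of sotorasib on Days 1, 4 and 7", so the last one falls on Day 6 after a Day 4 dose and on Day 9 after a Day 7 dose. Those are the two end-of-study days.

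**Window per dose.**
- Day 1 to Day 4: 3 × 24 = 72 h
- Day 4 to Day 7 (the 14 subjects): 72 h
- Day 4 to end of study on Day 6 (the other 146 − 14 = 132 subjects): 48 h
- Day 7 to end of study on Day 9 (Treatment C): 48 h

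**Mean window per treatment.** Let k of the 14 come from Group 2 (B then A).

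A = [73×72 + k×72 + (73−k)×48] / 146

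B = [73×72 + (14−k)×72 + (59+k)×48] / 146

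| k | A (h) | B (h) | C (h) | C/A | C/B |
|---|---|---|---|---|---|
| 7 | (5256+504+3168)/146 = 61.15 | 61.15 | 48 | 0.785 | 0.785 |
| 0 | 60.0 | 62.3 | 48 | 0.80 | 0.77 |
| 14 | 62.3 | 60.0 | 48 | 0.77 | 0.80 |

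Within the 14 subjects, A and B each have 72 h and C has 48 h, a ratio of 0.667.

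**Effect on counts.** Only events that start 48 to 72 h after a dose are affected. The documents give no onset distribution, so I assume that the share of onsets by time t is F(t) = 1 − 2^(−t/h), with h the median onset, and add a constant-rate case. With k = 7, a share w = 80/146 = 0.548 of A doses has 72 h.

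Share of A's events outside C's window:
- within the 14 subjects: 1 − F(48)/F(72)
- planned table: 1 − F(48)/[w·F(72) + (1−w)·F(48)]

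For example, at h = 24 h, F(48) = 0.75 and F(72) = 0.875. This gives 1 − 0.857 = 14.3% within the 14, and 1 − 0.75/0.8185 = 8.4% in the planned table.

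| Assumed onset | Planned table | Within the 14 |
|---|---|---|
| h = 6 h | 0.2% | 0.4% |
| h = 12 h | 2.7% | 4.8% |
| h = 18 h | 5.8% | 10.1% |
| h = 24 h | 8.4% | 14.3% |
| h = 48 h | 13.8% | 22.7% |
| Constant rate | 21.5% | 33.3% |

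**Can a 48-h filter be built from what is collected?** SAP 8.6.1 already derives onset time from dosing. Two limits apply. First, Protocol Appendix 1 records an event whose severity changes once, at its worst severity, and lists onset and resolution dates but no worsening date. Second, an incomplete start gives only a minimum onset. In the SAP's own example (dose at 08:00 on 1 May, event dated 3 May without a time), the minimum shown is 40 h, but the event could have begun up to 63 h 59 min after dosing. A filter applied to the minimum would admit it.

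**The case against.** Most of the case against goes to size and importance, and much of it stands.

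- **The main contrast is nearly balanced.** The safety objective names the 3 x 320 mg and 8 x 120 mg tablets. The Period 3 objective is pharmacokinetic. Fed versus fasted safety is not a named comparison, and C is given last, unrandomised, to 14 subjects, so it is confounded with period whatever the window. This stands.
- **Drug-related events probably start early.** Protocol 1.2 gives tmax of 1 to 2 h, no accumulation on daily dosing, and comparable fed and fasted Cmax at 360 mg. Most reactions listed in Protocol 1.4.1.2 are gastrointestinal. Scheduled laboratory tests fall about 48 h after each dose (Days 3, 6 and 9), so laboratory-detected events are less affected. This favours the upper rows of the table above but does not settle the point, because the tables count all TEAEs.
- **Few subjects are involved.** If 20% of the 14 had a TEAE within 72 h (an assumption; 2.8 subjects), a loss of 5% to 33% is 0.1 to 0.9 of a subject.
- **Late events are already visible.** All AEs are listed with onset time, and treatment-related TEAEs are tabulated separately. That helps someone who reads the listings, but it does not make the summary columns comparable.

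A reader might infer three stronger things. One is that the planned table loses 33% of events; that figure belongs to a 14-subject comparison that the SAP does not plan, at a constant rate. Another is that A and B are always observed for 72 h; for 132 of 146 subjects the Period 2 dose is also the last and has 48 h. The third is that the 30-day SAE tail falls on C, so that 1 − 3/30 = 90% of background SAEs credited to C lie outside A's window. No rule assigns post-study SAEs to any treatment, the SAP 8.1 cut-off leaves open whether they are reported at all, and the last treatment is A or B for those 132 subjects.

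**Conclusion.** The point holds for non-serious TEAEs. The direction is fixed by the design: C's counts are biased downward against both A and B. The window ratio is about 0.785 in the planned tables (0.77 to 0.80 across possible splits of the 14) and 0.667 within the 14 subjects. The loss of events cannot be fixed from the documents. It is small if onset is mostly within 12 h and reaches 21.5% (planned table) or 33% (within the 14) only at a constant rate. These figures assume full planned enrolment, dosing and end of study at about the same time of day, and the onset models shown.

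For SAEs the finding is narrower: the attribution of events after end of study is unspecified. No size can be put on that. The A versus B safety comparison is close to balanced, and the bioequivalence conclusion is untouched. This is a low-cost improvement to descriptive reporting.

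**What to change.** In SAP 8.6.1:

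1. Keep the planned all-TEAE tables by treatment and state each treatment's observation window in the header or a footnote. They remain the main A and B tables, so no late event is removed from them.
2. Add one table of TEAEs with onset within 48 h of each dose, showing C against A in the 14 Period 3 subjects. Every scheduled window is then 48 h and the ratio is 1.00.
3. Filter on derived onset time only. Say that events which qualify as TEAEs only by worsening stay in the all-TEAE tables, because no worsening date is collected.
4. State in advance how an onset shown with ≥ enters the filter, and footnote how many events the rule affects.
5. List SAEs that start after end of study separately, with time since last dose and the last treatment received, and say whether they enter any by-treatment table.

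The cost is SAP wording, one filter on an existing variable and one extra descriptive table, with no new visit or data item. The added table covers 14 non-randomised subjects and is still confounded with period; it removes the window difference and nothing else.

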## 8.4. Safety Analysis

The number and percentage of subjects reporting any adverse events will be tabulated by Medical Dictionary for Regulatory Activities system organ class and preferred term. Tables of fatal adverse events, serious adverse events, adverse events leading to withdrawal from investigational product or other protocol-required therapies, and significant treatment-emergent adverse events will also be provided. Subject-level data may be provided instead of tables if the subject incidence is low.

Endpoints for clinical laboratory tests, ECG, and vital signs will be summarized.

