#### **Recording Adverse Events and Serious Adverse Events**

#### Adverse Event and Serious Adverse Event Recording

- When an adverse event or serious adverse event occurs, it is the responsibility of the Investigator to review all documentation (e.g., hospital progress notes, laboratory, and diagnostics reports) related to the event.
- The Investigator will then record all relevant adverse event/serious adverse event information in the Event electronic Case Report Form (eCRF).
- The Investigator must assign the following adverse event attributes:
  - Adverse event diagnosis or syndrome(s), if known (if not known, signs or symptoms);
  - Dates of onset and resolution (if resolved);
  - Did the event start prior to first dose of investigational product, other protocolrequired therapies;
  - Assessment of seriousness;
  - Severity (or toxicity defined below);
  - Assessment of relatedness to the investigational product(s) and/or studymandated procedures;
  - Action taken; and
  - Outcome of event.
- If the severity of an adverse event changes from the date of onset to the date of resolution, record as a single event with the worst severity on the appropriate eCRF.
- It is not acceptable for the Investigator to send photocopies of the subject's medical records to Sponsor in lieu of completion of the appropriate eCRF page.

- If specifically requested, the Investigator may need to provide additional follow-up information, such as discharge summaries, medical records, or extracts from the medical records. In this case, all subject identifiers, with the exception of the subject number, will be blinded on the copies of the medical records before submission to the Sponsor.
- The Investigator will attempt to establish a diagnosis of the event based on signs, symptoms, and/or other clinical information. In such cases, the diagnosis (not the individual signs/symptoms) will be documented as the adverse event/serious adverse event.

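### The SAP's once-per-preferred-term rule is applied to the number of TEAEs as well as to subject counts, so the event column is not a count of events (minor; descriptive safety tables only)

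*SAP*

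**What the plan says.** SAP Section 8.6.1 (Adverse Events) introduces its main TEAE tables with "The frequency of subjects with TEAEs and the number of TEAEs will be summarized for the following categories". The categories are all TEAEs together with the serious, discontinuation and fatal subsets; TEAEs by severity; and the same two sets for treatment-related TEAEs. All are by treatment.

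The tables by system organ class and preferred term are introduced differently: "The frequency of subjects will be summarized separately for TEAEs and treatment-related TEAEs by the following". No event count is planned there.

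Later in the same section comes the counting rule. It opens "For the calculation of TEAE summary statistics: If a subject experienced" and continues "multiple TEAEs with the same preferred term for the same treatment, this will be counted as 1 TEAE for that treatment", with the maximum recorded severity kept. It is not restricted to any table or column.

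Three other provisions matter:

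- SAP 8.6.1 also provides that "All AEs will be listed", with derived onset time and duration.
- Protocol Section 8.4 commits only to incidence: "The number and percentage of subjects reporting any adverse events will be tabulated".
- Protocol Appendix 1 already handles a change of severity within one event, telling the investigator to "record as a single event with the worst severity on the appropriate eCRF".

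**The concern.** The SAP distinguishes subjects with TEAEs from numbers of TEAEs, then gives one counting rule that suits only the first. Collapsing repeats and keeping the worst grade is the usual convention for a subject-incidence table. An event count normally adds what incidence leaves out, namely how often things happened.

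Safety and tolerability of the two tablet presentations is a secondary objective (Protocol Section 2.1). The reactions listed under Risks of Sotorasib (Protocol Section 1.4.1.2) include diarrhea, nausea and vomiting, which can occur more than once after a dose. A reader of the study report would take a column headed as the number of TEAEs at face value. At stake is whether that column means what its label says.

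**Working it through.** The plan states no figure for this point, so there is nothing to reproduce. The check is a reading of the text, followed by simple counting.

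**Step 1: scope of the rule.** The opening words, "For the calculation of TEAE summary statistics: If a subject experienced", cover every TEAE summary. The rule says that the events count as one TEAE; it does not say that the subject is counted once. The only tables that promise a number of TEAEs are the overall and by-severity tables and their treatment-related versions, and nothing exempts them.

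**Step 2: what is merged.** A single event whose grade changes is already one eCRF record under Protocol Appendix 1. What the SAP rule merges is therefore separately recorded events. The merging is within treatment: "Subjects will receive a single dose in each treatment period, on Days 1, 4, and 7" (Protocol Figure 1 footnote). A term that recurs under another treatment is counted again.

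**Step 3: size of the shortfall, in general.** Let k be the number of recorded events for one subject, one preferred term and one treatment.

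- True number of events = sum of k over all subject-term pairs with k of at least 1.
- Number under the SAP rule = number of such pairs.
- Shortfall = sum of (k - 1) over those pairs.

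For any single term, the event count therefore equals the subject count and carries no information on recurrence.

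**Step 4: illustration with assumed figures.** Ten subjects have the same term under one treatment:

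| Episodes per subject | True events | SAP count | Subjects |
|---|---|---|---|
| 1 | 10 | 10 | 10 |
| 2 | 20 | 10 | 10 |
| 3 | 30 | 10 | 10 |

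By severity: suppose one subject has two grade 1 records and one grade 2 record of the same term under one treatment. The true event counts are 2 at grade 1 and 1 at grade 2. The SAP rule gives 0 and 1.

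**Step 5: range under an assumed recurrence model.** If episodes are Poisson with mean λ per subject, term and treatment, the SAP count divided by the true count is (1 - exp(-λ))/λ.

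| λ (assumed) | SAP count / true count |
|---|---|
| 0.02 | 0.990 |
| 0.05 | 0.975 |
| 0.1 | 0.952 |
| 0.2 | 0.906 |
| 0.5 | 0.787 |
| 1.0 | 0.632 |

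The documents give no value for λ and no support for the Poisson form. The table shows only how the shortfall grows with recurrence.

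**The case against.** The case for leaving the text alone has several parts.

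- **The protocol commitment is met.** Protocol 8.4 promises subject counts, which the rule leaves intact. That is true. But the SAP adds the event count, and SAP Section 1 says that the SAP takes precedence over the protocol on statistical matters. A statistic that is planned should be what it is called.
- **The rule is pre-stated and keeps the worst grade.** It is explicit, but the SAP nowhere tells the reader that its number of TEAEs is a count of subject-by-term pairs.
- **The table shells may settle it.** SAP Section 1 refers to a separate shells document, which was not available for this review. It may restrict the rule to subject columns. That could resolve the matter in practice, but it would not change what the SAP says.
- **Repeats may be few.** Each treatment is a single dose, with doses three days apart, and at low assumed recurrence (λ from 0.02 to 0.1) the shortfall is about 1% to 5%. This is a fair point about size, and it stands.
- **Nothing depends on the column.** No inferential safety analysis is planned (SAP 8.6.6), and the withdrawal and pause criteria in Protocol Section 4.5 turn on individual subjects and events. This also stands.

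A reader might go further and infer that recurrent reactions are under-reported in the trial. The documents do not support that. Every recorded event is listed, incidence is unchanged, and repeats under a different treatment still count. Nor can a percentage loss be taken from a constructed subject. Someone with three vomiting and two diarrhea records would show 2 instead of 5, but that describes the invented case and not this study.

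**Conclusion.** Wrong as written, but minor. Followed literally, SAP 8.6.1 yields a number of TEAEs that is the number of subject-by-preferred-term pairs per treatment. It is too low by k - 1 for each subject, term and treatment with k recorded events, and the by-severity event counts lose the lower-grade repeats. It is correct only if no subject has the same term recorded twice under the same treatment.

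The actual shortfall cannot be computed, because no recurrence rate is given. The conclusion rests on reading the rule as worded and on repeat episodes being entered as separate eCRF records. The effect is confined to one column of descriptive safety tables. The bioequivalence and food-effect analyses and the sample size are not touched.

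A reader might also expect that correcting the rule would reveal, for example, more vomiting episodes under one tablet presentation. It would not do so directly: event counts are planned only for pooled categories and by severity, and the preferred-term tables give subjects only. Episodes of a particular term would still have to be read from the listings.

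**What to change.** In SAP 8.6.1, replace the counting rule with one that separates the two statistics, for example: *For subject counts, a subject with several TEAEs of one preferred term under one treatment is counted once, at the highest severity. For the number of TEAEs, every TEAE record is counted, at its own severity.*

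If the sponsor prefers to keep the collapsed count, the fallback is to relabel the column as distinct preferred terms per subject and to footnote the rule. In either case, check that the table shells agree.

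The cost is one sentence in the SAP and a minor programming change. No new data are needed, and subject frequencies do not change.
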